SAFER: A Brief Intervention Involving Family Members in Suicide Safety Planning

Study Protocol and Statistical Analysis Plan

While support for involvement of family members in care has to address suicide risk been discussed in many national trainings for VA mental health ([name], personal communication), this work has been hampered by the lack of research on effective conjoint interventions to address suicide risk in adults. To date, we are aware of only one intervention study evaluating a relative-inclusive intervention to address suicide risk in adults (Anastasia, Humphries-Wadsworth, Pepper, & Pearson, 2015). Though this trial has positive results, it tested a hospital division program including primarily females, so its generalizability to a primarily male outpatient Veteran population is unknown.

To fill this gap in research and clinical care, Safe Actions for Families to Encourage Recovery (SAFER) was developed.

The Safe Action for Families to Encourage Recovery (SAFER) intervention is a family-based SPI treatment. Specifically, SAFER aims to help Veterans cope more effectively, improve communication, limit feelings of burdensomeness while building a more robust support system and sense of belonging, all in the service of lessening suicide risk. Simultaneously, for families, SAFER targets their support of Veteran coping, communication, and lessens feelings of being burdened by the Veteran.

The SAFER intervention was developed as a manualized, 4-session 90-minute dyad-based approach that includes psychoeducation about suicide risk and focuses on building a Veteran and supporting partner safety plan (see **Table 1**). Open label pilot testing of the intervention on six Veteran couples enabled the research team to finalize the manual and session content and resulted in promising feasibility and acceptability data on the dyad format. In order to test the initial efficacy of the SAFER intervention, a small randomized clinical trial was

designed comparing SAFER to a control condition – individual Safety Planning Intervention (I-SPI) that entailed creating a safety plan individually and is the standard of care in VA practice.

The specific hypotheses of this randomized control trial were:

Study Hypotheses

Hypothesis 1. Veterans participating in SAFER will experience reduced severity of suicidal ideation in comparison to Veterans completing I-SPI.

Hypothesis 2. Veteran-supporting partner dyads participating in SAFER will show improved suicide related coping in comparison to I-SPI. Specifically, we predicted Veterans would experience improvement in suicide-specific coping (Hypothesis 2A) and the supporting partner would demonstrate greater resource knowledge and support of Veteran’s coping efforts (Hypothesis 2B).

Hypothesis 3. Veteran- supporting partner dyads participating in SAFER will show reductions compared to I-SPI on interpersonal appraisals that are related to suicide risk. Specifically, we predicted Veterans would experience reduced perceived burdensomeness and thwarted belongingness (Hypothesis 3A) while supporting partners would experience reduced caregiver burden (Hypothesis 3B).

Methods

Overview

The study is designed as a randomized controlled study comparing SAFER to I-SPI in a sample of thirty-nine Veteran-supporting partner dyads struggling with recent or past suicidal ideation. Outcomes were evaluated using two follow-up assessments (post-treatment and extended follow-up) that were. Due to the difficulty of recruiting this specialized sample, participants were re-contacted for a given assessment until it was finally completed. All

procedures and instruments were approved by an institutional review board. Given the novel nature of the SAFER intervention, the sample intentionally was recruited for having moderate to high, but not extreme immediate risk.

Participants

Eligible Veterans were at moderate risk for suicide, defined as: having endorsed recent passive or active suicidal ideation (within the past 3 months) or a lifetime history of a suicide attempt. Additionally, Veterans must have been receiving care at the VA and have had an available, consenting, and qualifying supporting partner to participate. Supporting partners needed to meet at least three (two for nonrelatives) of five criteria inclusion criteria established by (Pollak & Perlick, 1991): 1) is a spouse, co-habiting significant other or parent; 2) has more frequent contact than any other caregiver; 3) helps to support the patient financially; 4) is contacted by treatment staff for emergencies; 5) has been involved in the patient's treatment.

Veterans and supporting partners were excluded if: 1) history of suicide attempt in the past 3 months; 2) they presented with untreated or un-medicated active psychosis; 3) they presented with alcohol or drug abuse or dependence within the past month; 4) they presented with medical condition or life event (e.g., an upcoming move to another state) that would compromise participation; 5) they recently (past 6-months) participated in another family-based psychosocial intervention trial ; 6) had limited English proficiency; 7) and if they were participating with a romantic partner and endorsed recent, "severe" intimate-partner violence. Participants were screened for inclusion/exclusion with measures described below immediately after consent.

To determine inclusion/exclusion the Patient Health Questionnaire (PHQ; Spitzer, Kroenke, & Williams, 1999) was used to screen for alcohol or drug abuse or dependence within

the past month, defined by criteria met on the PHQ's modules of alcohol and drug abuse or dependence. For romantic couples, to determine recent, "severe" intimate-partner violence, the revised 20-item Conflict Tactics Scale Short Form (CTS2S; Straus & Douglas, 2004) was used.

The study aimed to recruit, consent, and randomize 40 Veterans at risk for suicide and 40 corresponding supporting partners over a 30-month period from a large VA medical center in a major metropolitan area in the North East. Recruitment sources included VA suicide prevention coordinators, a Veteran's primary clinician from the VAMC's psychiatric inpatient unit or outpatient care center, or through community outreach (e.g., Vet Centers and higher education institutions).

Procedure

Assessments

After screening and consent, Veterans and supporting partners completed separate in-person baseline assessments which included demographic data, Veteran and supporting partner assessments to assess inclusion/exclusion, and measures including the final study outcomes. Each Veteran-supporting partner dyad was then randomly assigned to participate in either I-SPI or SAFER with a one to one ratio using a block randomization scheme. Regardless of randomization, Veterans were allowed to continue with all other VA care, as needed. Outcomes were re-assessed immediately post-intervention and then again through a follow-up assessment at least 3-months post-intervention. To minimize attrition in this difficult to obtain and track sample, participants were initially contacted at the end of their intervention and then re-contacted until one or both provided the post-treatment assessment (Range=0.30-7.47 months from baseline; $M=2.84$ months) and then the follow-up was timed three months from that point or up

until one year from enrollment (Range=3.10-11.43 months from participants' baseline; $M=6.32$ months).

Attrition. Of the 78 participants in the study, 57 gave at least one wave of follow-up (30 Veterans; 27 Supporting Partners). Examination of demographic predictors of attrition found that participants who provided follow-up did not significantly differ from participants who did not with respect to assigned condition, years of education, gender, ethnicity, race, employment status, nature of caregiving relationship, Veteran status of the non-Veteran partner, or any of the baseline levels of the outcome measures. However, age did significantly predict attrition ($t(76) = -2.36; p < .02$), with those providing follow-up being generally older ($M=51.37$ years) than those who did not ($M=42.76$ years).

Individual Suicide-Safety Planning (Control)

As noted above, all participants were able to continue in standard VHA care based on their own determined needs (psychiatry; psychotherapy; and case management by the suicide prevention coordinator). Veterans in the control group were able to update and review their safety plan with a study clinician. Veterans created a full SPI with a study clinician if they did not already have one.

SAFER Intervention (Treatment)

The SAFER intervention is a novel, manualized, 90-minute dyad-based intervention that typically includes a joining session, two treatment sessions, and a booster. SAFER follows standard skills training session format and include: 1) brief check-in with brief assessment of mood, current level of suicidality and use of safety plan; 2) homework review; 3) teaching of new material and skill; 4) in-class practice of the skill; and assignment of homework/outside practice of skill /development of safety plan. Session content includes the use of psychoeducation,

communication skills training and revision and development of both the Veteran and a complementary supporting partner SPI. The SAFER treatment goal is to provide the tools and structure to support social support involvement in Safety Planning Intervention for Veterans at moderate risk for suicide (**Table 1**).

Treatment Fidelity. A fidelity scale was developed during the prior open trial plot testing to assess core features of SAFER's structure, contents and treatment principles, along with general clinical competence (e.g., building rapport, crisis management, etc.). This 14-17 item scale (13 general competence items and 1-4 session-specific items) was rated on a 4-point Likert scale (where 0 = unacceptable and 3 = excellent). were made by one trained rater. The rater was trained by the Principal Investigator and research staff. It was a one-day training to review components of the treatment manual, instruction in group therapy principles and group didactics, and suicide risk assessment. Additionally, the rater read the 51-page manual inclusive of session handouts and worksheets. All intervention sessions were recorded, and a randomization scheme was generated to have seven sessions randomly selected for review. Clinicians are required to maintain a total score of 80% or above on each session to demonstrate acceptable adherence to the intervention. Clinicians whose ratings fall below this criterion were given additional supervision and their adherence was monitored until satisfactory adherence was regained. The average percentages on the adherence scale ranged from 82 to 100 with the mean score being 90.7. No interventionists ever dropped below the 80% adherent threshold and therefore no re-training was required throughout the trial.

Measures

Primary Outcome Measure (Hypothesis 1)

Veteran suicidal ideation. Moderate suicidality was measured to determine eligibility

using the Columbia Suicide Severity Rating Scale (C-SSRS). Posner and colleagues (2011) found the C-SSRS to have divergent validity, predictive validity, sensitivity, specificity, sensitivity to change, and internal consistency in a multisite study (Posner, et al., 2011). The C-SSRS was also used across time points to record level of ideation, lifetime suicide attempts, and recent suicide attempts. Research staff was trained by [name] and [name], two of the developers of the assessment. Additionally, staff had weekly meetings in which the C-SSRS was discussed to ascertain consensus when scenarios warranted further discussion.

Suicide-Specific Coping (Hypothesis 2)

Veteran suicide-related coping. Suicide-related coping was evaluated by the Suicide-related Coping Scale (SRCS), a 17-item self-report measure assessing one's ability to cope with suicidal ideation and urges (Stanley, Green, Ghahramanlou-Holloway, Brenner, & Brown, 2017). The scale demonstrated good internal consistency ($\alpha=.85$) at baseline; scores were summed so that higher scores represent greater confidence and breadth of approaches to coping with suicidal thoughts and feelings.

Partner's support of suicide-related coping. Supporting partners also completed five items adapted from the SRCS that assessed their confidence in their ability to support the Veteran through their suicidal urges. The five items were, "I know the nearest hospital or urgent care facility where my loved one can go if I cannot handle the crisis on my own," "When my loved one is feeling suicidal or showing signs of suicidal thinking/behavior, there are places we can go to help take his/her mind off the problems," "I have several things I can do to help my loved one get through a suicidal crisis," "I am able to put aside my own fears and focus on taking appropriate actions when my loved one is feeling suicidal or showing signs of suicidal

thinking/behavior,” and “Seeking help from health care professionals is a good way to keep my loved one safe when he/she is feeling suicidal or showing signs of suicidal thinking/behavior.” Items were rated on a 0 (*Strongly Disagree*) to 4 (*Strongly Agree*) and were summed so that higher scores indicated greater self-efficacy when supporting the Veteran through suicidal crises, In addition to face validity, the scale showed acceptable internal consistency in the sample ($\alpha=.78$).

Suicide-promoting appraisals (Hypothesis 3)

Veteran perceptions of burdensomeness and thwarted belongingness. Perceived burdensomeness and thwarted belongingness were evaluated by the Interpersonal Needs Questionnaire (INQ-15; Van Orden, Cukrowicz, Witte, & Joiner, 2012). Scores on each subscale are summed so that higher scores represent a greater degree of Perceived Burdensomeness ($\alpha=.95$) and Thwarted Belongingness ($\alpha=.79$).

Supporting partner’s experience of caregiver burden. Caregiver burden was evaluated using the Caregiver Burden Inventory (CBI; Novak & Guest, 1989), a 24-item scale assessing caregiver burden in five areas: time, physical, social, developmental and emotional burden. Items were summed to create an overall measure of caregiver burden ($\alpha=.94$).

Analytic Strategy

We examined predicted trajectories on the outcomes of interest using slope-intercept trajectories based on Hierarchical Linear Modeling (HLM; Raudenbush & Bryk, 2002). We specifically created a two-level model in which repeated measurements over time were modeled at Level 1 (within-person change) and differences between participants/dyads were modeled at Level 2 (between-person change, including difference in condition).

$$\text{Level 1} \quad \text{Outcome} = \pi_0 + \pi_1 * (\text{months since baseline}) + E$$

The Level 1 equation represents a slope-intercept model predicting each participants' estimated score on an outcome baseline (π_0) and then calculating linear change in that outcome each month across the study (π_1). Slope-intercept trajectories are ideal for the present data given the variable assessment windows across all participants and the ability of HLM to use all available information from each participant to estimate these slopes using restricted maximum likelihood estimation.

$$\begin{aligned} \text{Level 2} \quad \pi_0 &= \beta_{00} + \beta_{01}*(\text{Condition}) + \beta_{02}*(\text{Veteran History of Attempt}) + \\ &\quad \beta_{03}*(\text{Relationship with Supporting Partner}) + \beta_{04}*(\text{Age}) + r_0 \\ \pi_1 &= \beta_{10} + \beta_{11}*(\text{Condition}) + \beta_{12}*(\text{Veteran History of Attempt}) + \\ &\quad \beta_{13}*(\text{Relationship with Supporting Partner}) + \beta_{14}*(\text{Age}) \end{aligned}$$

The Level 2 equation models respondents' trajectories based on condition (SAFER=1; I-SPI=0). Due to limited power, we were sparing with our controls and limited them to those considered most relevant to Veteran risk (history of attempt; 0= No attempts; 1=Has 1+ attempts), ability to collaborate with the supporting partner (nature of relationship between partners; 1=Romantic; 0=All others), and attrition (age). The treatment effect of SAFER is modeled as the effect of condition on change in functioning over time (β_{11}) after controlling for differences between conditions at baseline (β_{01}) and demographic controls (all other β s).

As Veterans and supporting partners were assessed on separate outcomes that in many cases were assessed weeks to months apart from one another, we estimated separate trajectories for each outcome without needing to account for dyadic dependence.

Results

Descriptives

Participant characteristics at baseline can be found on Table 3. Consistent with the Veteran population in the recruitment region, the sample was generally middle-aged, more likely to be black, somewhat more likely to be Hispanic/Latino and somewhat more likely to be unemployed than the general population. The final sample of 39 Veteran-supporting partner dyads included a range of supports including 14 romantic partners, 13 family members of Veterans, and 12 close friends. Although supporting partners were not required to be Veterans, a third of supporting partner (n=13) identified as Veterans themselves. 19 Veterans reported a history of one or more suicide attempts. As can be seen on Table 3, participants were generally similar across both conditions with respect to demographics characteristics as well as all outcomes. This highlights the effectiveness of random assignment in our small sample and suggests the groups are roughly comparable for treatment analyses.

Impact of Treatment Condition on Change in Outcomes over Time

The full model examining change in C-SSRS rated severity of suicidal ideation can be found in **Table 4**. As can be seen in the top half of **Table 4**, Veteran suicidal ideation did not significantly differ at baseline by condition or demographic controls. However, there was a significant effect of treatment condition on their trajectories over the course of the study. Specifically, Veterans in the active SAFER condition were predicted to see sharper declines in suicide ideation than those in the control group ($B = -0.37$; $p = .032$). In order to clarify the impact of treatment on trajectory over time, we then calculated the slope-intercept trajectory within each condition. Veterans in the SAFER condition experienced significant declines in severity of suicidal ideation while there was little change over time in the control condition.

This pattern of findings was replicated when examining the impact of treatment participation on coping strategies (Hypothesis 2). Specifically, a significant treatment-by-time

interaction emerged when predicting Veteran suicide-related coping ($B=1.40$; $p=.028$).

Examination of simple slopes highlights that Veterans in SAFER reported marginal increases in suicide-related coping (Simple Slope= 0.88 ; $p=.080$) while Veterans in I-SPI reported non-significant declines in coping. Similarly, a treatment effect emerged for supporting partners support of Veteran coping ($B=0.79$; $p=.034$). Specifically, while supporting partners in I-SPI provided marginally less support over time, caregivers in SAFER maintained their efforts to support Veteran coping.

Contrary to expectations, self-reported appraisals of relational factors and self-efficacy were not impacted by condition for either Veterans or supporting partners. In fact, modeling trajectories across both conditions highlight that most appraisal variables are expected to be stable across the length of the study.

Impact of Controls

Although not part of our primary hypotheses, we examined significant effects of controls on the outcomes of interest. Notably, romantic partners of Veterans reported substantially higher overall levels of caregiver burden at baseline ($B=17.66$; $p=.01$) that remained relatively stable over the study. Veterans with romantic partners showed corresponding increases in suicide ideation severity ($B=0.49$; $p=.02$; Table 2) and decreases in suicide-related coping ($B=-1.52$; $p=.04$). In contrast, Veteran history of suicide attempt was associated with only somewhat elevated caregiver burden on baseline ($B=7.22$; $p=.28$) that were offset greater declines in caregiver burden over the study ($B=-2.38$; $p=.03$). Taken together, this indicates that caregivers of Veterans with a history of attempt showed general adaptation as the crisis subsided while romantic partners of Veterans experienced stable high levels of burden that were then followed by worsening functioning for the Veteran over time.

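### Do an 80% total score and seven reviewed sessions leave SAFER adherence so poorly shown that the plan must change?

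*Combined protocol and SAP*

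**What the plan says.** Under Treatment Fidelity, the combined protocol and SAP describes a "14-17 item scale (13 general competence items and 1-4 session-specific items", each item rated 0 (unacceptable) to 3 (excellent) by one trained rater. The scale as a whole is said to cover SAFER's "structure, contents and treatment principles, along with general clinical competence". The criterion is a total: "Clinicians are required to maintain a total score of 80% or above on each session to demonstrate acceptable adherence to the intervention". The sentence just before it gives the amount of checking: "a randomization scheme was generated to have seven sessions randomly selected for review". Clinicians with a rating under the criterion were to receive more supervision until adherence recovered.

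Two results follow: "The average percentages on the adherence scale ranged from 82 to 100 with the mean score being 90.7" and "No interventionists ever dropped below the 80% adherent threshold and therefore no re-training was required throughout the trial". No sub-score for the session-specific items is reported, and the unit of the averages (session or clinician) is not stated.

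**The concern.** Two things look wrong at first.

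- **The total may not measure what it is said to measure.** If most of the points come from general clinical skill, a clinician could pass while failing every item tied to the content of that session. A reader would then take 82 to 100% as proof that SAFER content was delivered when the score does not by itself show it.
- **The conclusion reaches further than the sample.** The rule applies to each session, but only seven were rated. Saying that nobody ever fell below 80%, across the trial, is a statement about sessions that nobody scored.

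At stake is how far a reader can attribute the reported differences between arms to SAFER as designed.

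**Working it through.** **The reported figures.** The seven scores are not given, so 90.7 cannot be recomputed. If the figures are per session, it is at least consistent with the range: 7 × 90.7 = 634.9, and (634.9 − 82 − 100)/5 = 90.58 for the other five sessions, which lies between 82 and 100.

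**What the total allows.** Inputs from Treatment Fidelity: 13 general items, k = 1 to 4 session-specific items, 0 to 3 points each, pass at 80%. I read the percentage as points out of the maximum, which is the natural reading but is not spelled out.

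- Maximum total = 3 × (13 + k)
- Pass mark = 80% of the maximum, rounded up to a whole point
- Highest total with zero on all session-specific items = 3 × 13 = 39

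| Items | Maximum | Session-specific share | Pass mark | 39/maximum | General points needed if session-specific = 0 |
|---|---|---|---|---|---|
| 14 | 42 | 3/42 = 7.1% | 34 | 92.9% | 34/39 = 87.2% |
| 15 | 45 | 6/45 = 13.3% | 36 | 86.7% | 36/39 = 92.3% |
| 16 | 48 | 9/48 = 18.8% | 39 | 81.3% | 39/39 = 100% |
| 17 | 51 | 12/51 = 23.5% | 41 | 76.5% | not possible; at least 2 of 12 session-specific points |

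So the gap exists on three of the four forms, but it needs an odd session: every session-specific item rated unacceptable alongside near-perfect or perfect marks on everything else.

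**What the reported low end allows.** If 82% is a single session with whole-number ratings, only two totals round to it: 37/45 = 82.2% and 42/51 = 82.4%. These permit session-specific scores of 0/6 to 6/6 and 3/12 to 12/12 respectively. The figure is compatible with poor session-specific ratings and equally with full marks. Nothing can be read from the mean in this way: it averages sessions that may be on different forms, and no whole-number total gives 90.7% on any form (nearest 38/42 = 90.5%, 41/45 = 91.1%, 44/48 = 91.7%, 46/51 = 90.2%).

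**What seven sessions support.** If scores are per session and sessions are independent, 0 of 7 below 80% has a one-sided 95% upper limit of 1 − 0.05^(1/7) = 34.8%. If 20% of sessions were truly below 80%, seven clean ones would occur with probability 0.8^7 = 21.0%; at 10%, 0.9^7 = 47.8%.

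For the sampling fraction I assume 19 or 20 SAFER dyads, since the 39 dyads were "randomly assigned to participate in either I-SPI or SAFER with a one to one ratio", and the full "4-session 90-minute dyad-based approach". That gives 19 × 4 = 76 to 20 × 4 = 80 sessions, of which seven is 9.2% to 8.8%. Allowing for the finite number of sessions, the upper limit is 25/76 = 32.9% or 26/80 = 32.5%.

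**Where the score is used.** The Analytic Strategy models each outcome on time, condition, attempt history, relationship and age. The treatment effect is the effect of condition on the monthly slope. The fidelity score is not a covariate, a weight or an inclusion rule.

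**The case for a change.** The strongest case for a change is that this paragraph is the only evidence in the document that SAFER was delivered as designed. Control Veterans also worked with a study clinician, so general skill does not set the arms apart; the SAFER content does. Two sub-scores for seven sessions and one tighter sentence would cost little.

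Part of this stands. A total of 80% does not by itself show that the session-specific items were rated acceptably. The closing sentence is worded more widely than seven ratings can carry. If the averages are per clinician, one rated session under 80% could be hidden even though the rule is per session.

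The rest does not carry. All 13 common items are unseen, and the section says the scale covers SAFER's structure and principles as well as general skill. The check-in, homework review, teaching, practice and homework assignment recur in every session and could reasonably sit among the common items. If they do, the total is a fair adherence measure and a sub-score of one to four items is not a better one. The re-training statement is procedurally sound: supervision was triggered by ratings, and if no rating fell below 80% the trigger did not fire. The denominator is stated in the same paragraph. A confidence limit in the text would assume per-session scores and independence, although sessions are nested in clinicians. Sub-scores depend on item-level ratings having been kept, which the document does not say.

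**Conclusion.** No change to the plan follows. A pass without any session-specific credit is arithmetically possible on three of the four forms (up to 92.9%, 86.7% and 81.3%), and seven clean sessions leave an upper limit of about a third of sessions below the threshold. Neither figure shows that fidelity was poor, and no session is shown to have passed that way. Rating a random sample of sessions against a composite cut-off is a fair trade-off in a trial of 39 dyads.

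The effect on the trial's estimates and p-values is nil, because the fidelity score feeds no analysis. Authors reporting the trial can sensibly confine the closing statement to the seven reviewed sessions, state whether 82 to 100 is per session or per clinician, and add descriptive sub-scores if the item ratings exist.

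This rests on three assumptions: the percentage is of maximum points, the sampling figures treat scores as per session and (for the 34.8% limit) sessions as independent, and the SAFER arm had 19 or 20 dyads with four sessions each.

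### The slope equation that carries the treatment effect has no person-level residual and no stated reason, so the standard error of beta_11 may be too small

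*Combined protocol and SAP*

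**What the plan says.** The Analytic Strategy sets out a two-level model with months since baseline at Level 1. At Level 2 the intercept equation ends in a person-level residual, r_0. The slope equation ends "\beta_{13}*(\text{Relationship with Supporting Partner}) + \beta_{14}*(\text{Age}) \end{aligned", with nothing after the age term.

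The text below the equations places the treatment comparison in that second equation: "The treatment effect of SAFER is modeled as the effect of condition on change in functioning over time", which is beta_11.

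On estimation, the section cites "the ability of HLM to use all available information from each participant to estimate these slopes using restricted maximum likelihood estimation". That names restricted maximum likelihood but not whether standard errors were model-based or robust. The reference to slopes for each participant also leaves it open whether a person-level slope term was fitted although not printed. The one remark about economy, that limited power kept the list of controls short, concerns covariates and not random effects.

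The Results section reports three positive treatment-by-time effects:
- C-SSRS ideation, where SAFER Veterans were predicted to see "sharper declines in suicide ideation than those in the control group ($B = -0.37$; $p = .032")
- Veteran suicide-related coping (B = 1.40, p = .028)
- partner support of coping (B = 0.79, p = .034)

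For the Hypothesis 3 outcomes it says that "self-reported appraisals of relational factors and self-efficacy were not impacted by condition".

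**The concern.** Without r_1, people who share the four covariates are assumed to change at exactly the same rate, and any departure is treated as independent visit-level noise. If people do differ in their rate of change, those departures persist within a person and grow with time. The model then credits the data with more information about slopes than they hold, and beta_11 appears more precise than it is.

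The study's own results make equal residual slopes an assumption that needs a reason. Under Impact of Controls, slopes differ by relationship type (ideation B = 0.49, p = .02; coping B = -1.52, p = .04) and, for caregiver burden, by attempt history (B = -2.38, p = .03). Veterans could also continue other VA care as needed. This is suggestive only, because those p values come from the same model.

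At stake are the three positive findings, one of them the primary outcome. The Hypothesis 3 outcomes, reported as unaffected by condition, are not threatened by a standard error that is too small.

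**Working it through.** **No figure to reproduce.** The text gives B and p but no standard error, degrees of freedom or variance components, and Table 4 is not in the text available. A corrected p value cannot be computed without the data. Two things can be checked: how much room each p value has, and how much slope variation would use it up.

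**What the missing term changes.** With r_0 only, the variance of an outcome at month t, given covariates, is tau0² + sigma², and the covariance between months t and u is tau0². With r_1 these become tau0² + 2t·tau01 + t²·tau1² + sigma² and tau0² + (t+u)·tau01 + t·u·tau1². The printed model sets tau1² and tau01 to zero.

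**Room in each p value.** With B and df held fixed, the break-even ratio is the critical value at the reported p divided by that at .05. For ideation the normal value is 2.144/1.960 = 1.094. The implied standard error is 0.37/2.144 = 0.173 (normal), or 0.37/2.236 = 0.166 (34 df = 39 dyads minus 5 Level 2 coefficients).

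| Outcome | Reported p | Break-even SE ratio (normal to 25 df) | p if SE is 20% larger (normal to 34 df) |
|---|---|---|---|
| Ideation | .032 | 1.094-1.103 | .074-.071 |
| Veteran coping | .028 | 1.121-1.133 | .067-.064 |
| Partner support | .034 | 1.082-1.089 | .077-.074 |

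**Slope variation needed.** Null trials were simulated and the printed model (10 fixed effects, random intercept, REML) was fitted.
- From the documents: 39 dyads; "57 gave at least one wave of follow-up (30 Veterans; 27 Supporting Partners"), so 39 - 30 = 9 Veterans and 39 - 27 = 12 partners have baseline only; visit times inside the stated ranges (simulated means 2.84 and 6.34 months, against the stated 2.84 and 6.32).
- Assumed: normal data; intercept SD of 0.5, 1 or 2 residual SDs; 60% or 100% of those followed having both waves; slope SD from 0 to 0.30 residual SDs per month; intercept-slope correlations of -0.5 and +0.5 tried at slope SDs 0.10 to 0.20 (80% with both waves). There were 12,000 replicates per setting.

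| Residual slope SD per month | True/reported SE, Veterans | Type I error, Veterans | Type I error, partners |
|---|---|---|---|
| 0 | 1.00-1.02 | 4-6% | 4-6% |
| 0.05 | 1.02-1.04 | 5-7% | 5-7% |
| 0.10 | 1.05-1.11 | 5-8% | 6-9% |
| 0.15 | 1.13-1.20 | 8-11% | 8-12% |
| 0.20 | 1.21-1.30 | 9-14% | 9-14% |
| 0.30 | 1.33-1.45 | 13-18% | 13-19% |

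Interpolating, break-even is reached at a slope SD of 0.09-0.13 for ideation, 0.11-0.15 for Veteran coping and 0.08-0.12 for partner support. With intercept SD equal to residual SD (baseline variance 1 + 1 = 2), the ideation value is 0.098-0.111. By 6.32 months that adds (0.098 × 6.32)²/2 = 0.19 to (0.111 × 6.32)²/2 = 0.25, or 19-25%, to the outcome variance.

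A separate simulation that scaled slopes by baseline SD, with intraclass correlation 0.5, gave a ratio of 1.15-1.17 at 0.10. In residual units that slope SD is 0.10/√0.5 = 0.14, so it agrees with the 0.15 row above.

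**Letting B move as well.** Trials with a printed-model p near the reported values were refitted with r_1 and Satterthwaite df (true effect 0.2, 80% with both waves). Among Veteran trials (p of .028-.036), p exceeded .05 in 23%, 40%, 57% and 77% at slope SDs 0, 0.10, 0.15 and 0.20. Among partner trials (p of .030-.038) it did so in 28%, 47% and 77% at 0, 0.10 and 0.20. The 23-28% at zero is the noise of re-testing itself.

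**The case against.** The harm needs three conditions: the printed model is the one fitted, the standard errors are model-based, and residual slopes vary enough. The available text establishes none of them, and Table 4 may settle the first two. That stands, and it makes the finding conditional.

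A random slope is also hard to estimate here, with at most three waves and 9 Veterans and 12 partners seen only at baseline. In simulation the r_1 fit was singular in 58% of trials at slope SD 0, 40% at 0.10 and 18% at 0.20. This could be a fair reason to leave r_1 out, but the documents do not give it. Weak estimability also does not make an r_0-only standard error valid.

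The upper end of the assumed range is probably extreme. With the standard error matched to the reported B and p (80% with both waves, intercept SD equal to residual SD), a slope SD of 0.30 is about 1.2 times B per month. On the 0-20 partner scale it would alone give an SD of about 6 points at 6.32 months. The largest figures should be discounted accordingly. Break-even, however, lies near 0.10, which is about half of B for ideation and partner support and is plausible.

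Lastly, a re-test can cross .05 by chance even when the printed model is right: 23-28% with r_1, and 30% with CR2 for Veterans. This stands as a limit on how the re-test is read, and it argues for qualifying a claim and not withdrawing it.

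**Conclusion.** The concern holds. The printed model assumes equal residual slopes in the equation that carries the treatment effect, with no reason given and the type of standard error unstated. If model-based standard errors were used and residual slopes vary, the reported precision is too high. At slope SDs of 0.05-0.10 the nominal 5% test has type I error of 5-8% for Veterans and 5-9% for partners; at 0.20 it is 9-14% for both. The margins of 8-13% on the three positive results are small enough for this to matter.

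If residual slopes do not vary, or robust standard errors were used, the point largely falls away. Because the slope SD is not given, this shows a risk to the three results and not an error in any of them. Confidence is moderate.

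**What to change.** State whether r_1 was in the fitted model and which standard errors produced the reported p values. If Table 4 already shows this, cite it.

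For ideation, Veteran coping and partner support, re-test beta_11 and the simple slopes in two ways:
1. Add r_1 to the slope equation, with Kenward-Roger or Satterthwaite df.
2. Keep the printed model, with CR2 cluster-robust standard errors by participant and Satterthwaite df.

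Name the first as the main re-test and the second as the one to use if the r_1 fit is singular, so that the choice does not depend on p. A singular fit should not be read as proof of equal slopes. In simulation, type I error was 4.6-4.7% (Veterans) and 5.8-6.1% (partners) for the first, and 4.5-6.2% for the second. CR3 should not be the only check: its type I error was 2-3%, and it moved 65% of trials with p near .032 past .05 even with no slope variation. Uncorrected robust standard errors are not enough at this size, with type I error of about 8-13%.

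Report B, SE, df and confidence interval from each. Where an outcome does not hold, say that its efficacy statement depends on the equal-slopes assumption. If fixed residual slopes are kept, give the reason.

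The cost is one model term, one alternative standard error and a re-run on existing data. The downside is probably wider intervals and less favourable p values. A p just above .05 on re-test would not prove that slopes differ.
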